### 6.4. Analysis of brain studies

### 6.4.1. Acquisition and analysis of functional MRI data

Stimuli for fMRI experiments will be photographs of appetizing (high-calorie) and bland (lowcalorie) foods, attractive and unattractive male and female faces, and nude male and female bodies. A number of fMRI studies indicate that the contrasting the viewing of such stimuli is a reliable way of activating the reward circuit (96)(97,98)(63). fMRI data will be acquired during a fasting state to maximize the hedonic value of the food stimuli. We will implement blood oxygenation level dependent (BOLD) contrast echo-planar imaging, in which the MR images are made sensitive to the state of oxygenation of haemoglobin (99). The variations of the BOLD signal reflect variations of the functional activity of neural networks (100). Hence, fMRI can be applied to localize ongoing neural activity during various cognitive and affective tasks. SPM5 software (www.fil.ion.ucl.ac.uk/spm/software/spm5) is used for the data analysis (84). First, functional images are sinc interpolated in time to correct for slice time differences and realigned to the first scan by rigid body transformations to correct head movements. Next the images are unwarped and a mean functional image is generated. EPI and structural images are co-registered and normalized to the MNI space using linear and non-linear transformations, and smoothed with a Gaussian kernel with 8 mm FWHM and analyzed with the general linear model (GLM).

## 6.4.2. Acquisition and analysis of structural MRI Data for VBM

High-resolution, anatomical images (1 mm^3 resolution) will be acquired using a T1-weighted sequence. Spatial normalization, tissue classification and radio-frequency bias correction are combined into a single step with segmentation to grey and white matter and cerebro-spinal fluid (101). Smoothed (10mm FWHM) and modulated grey and white matter images will be analyzed with GLM in SPM5 software.

## 6.4.3. Acquisition and analysis of DTI data

For DTI, 32 non-colinear directions of gradients are acquired to obtain the whole diffusion tensor with an echo-planar imaging (EPI) single-shot sequence. Data analysis will be carried out with FSL software (http://www.fmrib.ox.ac.uk/fsl/). Following brain extraction, the diffusion weighted images will be corrected for eddy currents and head motion. Subsequently, FA maps will be computed. Nonlinear registration will be employed to align the FA data across all subjects. FA maps will be analyzed using statistical parametric mapping (84). Probabilistic fibre tracking will be conducted using individually defined ROIs as source regions. Tract-based spatial statistics will be employed to compare the regions of the fibre tract skeleton where obese and lean individuals show different FA values.

### 6.4.4. Self-report measures

Reward drive will be measured with the BIS/BAS questionnaire (102). Self-reported hunger level will be measured with a visual analog scale, and food craving with the Food craving State / Trait (FCS-FCST) questionnaires (31). Depression will be measured with BDI-II (43), anxiety with the STAI form B (103), and external food sensitivity with the Dutch Eating Behavior Questionnaire (DEBQ) (104). Self-reports of hunger and mood will be obtained with the visual analogue scale. Questionnaires will be completed pre- and postoperatively and in all experiments we will analyze the effects of the obesity surgery on the self-report measures, and correlate the self-reports with functional and structural brain data.

### 6.4.5 Visual stimulation for fMRI

During the primary fMRI experiment, anticipatory food-related reward activity will be induced by showing the participants alternating 16s blocks of appetizing, high-calorie and bland, low-calorie food pictures. Periodically the participants are asked to evaluate their i) hunger level and ii) heart rate. In two control experiments, rewarding and nonrewarding control stimuli (bodies, faces and objects) will be presented using a similar design. All experiments will last approximately 12 minutes. Additional resting state block of 10 minutes will also be included. fMRI will be performed pre- and postoperatively. In the preoperative scan, testing for an interaction between the food type (appetizing vs. bland) and group (patients vs. controls) will reveal the components of the reward circuit that show enhanced responses to appetizing foods in obesity. BOLD signal changes due to viewing appetizing and bland foods will be correlated with striatal  $D_2R$  density.

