## 6.3.2.2 Functional MRI (fMRI) studies

The aim of the fMRI is to assess how bariatric surgery (sleeve/bypass) influences the brain reward system response to food stimuli. The main interest is whether bariatric surgery can specifically reduce the responses to appetizing, high-calorie foods and is there a difference in responses between the two surgical procedures. Reward drive will be measured using BIS/BAS-questionnaire. Self-reported hunger level will be measured with a visual analogue scale, and food craving with the Food Craving State / Trait (FCS-FCST) questionnaire (31). Before a control subject can participate in the fMRI study block, the possible factors affecting to the study outcome (i.e. eating disorder) are excluded using the same question forms used by the dietician for the obese patients.

Echo-planar imaging (EPI) protocol with Philips Gyroscan Intera 1.5T scanner will be used. Functional and anatomical volumes are collected with Philips Gyroscan Intera 1.5T CV Nova Dual scanner. High-resolution, anatomical images (1 mm^3 resolution) will be acquired using a T1-weighted sequence (TR=25 ms, TE=4.6 ms, flip angle 30°, scan time 376 s). Whole-brain functional volumes are acquired using blood oxygenation level dependent (BOLD) -weighted EPI sequence (TR=2998 ms, TE=50 ms, flip angle 90°, FOV=192 mm, matrix=64x64, bandwidth=62.5 kHz, slice thickness=4.0 mm, gap between slices=0.5 mm, 30 interleaved slices acquires in ascending order) sensitive to BOLD contrast. Manual responses will be acquired with a MRI compatible button box.

The stimuli consists of digitalized full-colour photographs depicting

- I. Appetizing, high-calorie foods (e.g. chocolate cake, sweets)
- II. Bland, low-calorie foods (e.g. cabbage, lentils)
- III. Non-food objects (e.g. cars, tools)

Fifty images from each category will be used. Stimulus presentation will be controlled with Presentation computer program (Neurobehavioral Systems Inc.) Stimuli are projected from an LCD projector onto a non-magnetic screen mounted at the foot of the scanner tube, and an angled mirror reflects the images on the screen to the participants' field of vision.

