The experiment will run with a classic blocked (box-car) design. Appetizing foods, bland foods and non-food objects will be presented in separate 15 second -blocks that consist of presentation of five pictures from the respective category. A 15 s rest period (fixation) will be intermixed between the stimulation blocks to reduce the activation of the reward systems back to baseline level and to enhance the power of the design. Each stimulus will be displaced slightly to the left or to the right from the centre of the screen and the participant has to detect the direction of the displacement and respond with a button press. This ensures that the participant has to pay attention to the stimuli. A total of 10 blocks per condition will be run, and the order of the blocks will be counterbalanced across the participants. The experiment lasts about 15 minutes. After the experiment, the participants will rate how appetizing the food stimuli were, using a scale ranging from 1 (not appetizing at all) to 10 (extremely appetizing).

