SPM5 software (www.fil.ion.ucl.ac.uk/spm/software/spm5) is used for the data analysis (84). First, functional images are sinc (sine cardinal) interpolated in time to correct for slice time differences and realigned to the first scan by rigid body transformations to correct head movements. Next the images are unwarped and a mean functional image is generated. The mean functional images are inspected for excessive signal dropout. EPI and structural images are co-registered and normalized to the T1 standard template in MNI space (95) using linear and non-linear transformations, and smoothed with a Gaussian kernel with 8 mm FWHM. A random effects model is implemented using a two-stage process of within (first level) and between (second level) –subjects modelling. This random-effects analysis assesses effects on the basis of inter-subject variance and thus allows making inferences from the population from where the participants were selected. For each participant a General Linear Model (GLM) is used to assess regional effects of task parameters on BOLD indices of activation. The model includes four experimental conditions (appetizing foods, bland foods, objects, rest) and effects of no interest (realignment parameters) to account for motionrelated variance. Low-frequency signal drift is removed using a high-pass filter (cut-off 128 seconds) and AR(1) modelling of temporal autocorrelations is applied. The individual voxel-wise tcontrast images are generated using the following contrasts:

- (1) Appetizing vs. bland foods
- (2) Bland vs. appetizing foods
- (3) Appetizing and bland foods vs. objects

These images are subsequently entered into a second-level model, subjected to a voxel-wise contrast and t-test using Gaussian Random Field Theory to assess whether or not the reward systems respond to high and low calorie foods in the experimental and the control group. A mixed ANOVA will be used to assess whether the responses of the reward system are different in the experimental vs. in the control group. The appetizing vs. bland foods contrast is used to assess the activation of the reward system in the experimental groups. The appetizing food vs. objects and bland foods vs. objects contrasts will be used to assess whether the gastric sleeve or gastric bypass surgery reduces the responses to appetizing foods only.

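### Sections 6.3.2.2 and 6.4.5 script the same food-picture fMRI experiment incompatibly, and the food-versus-object contrasts cannot be formed from the 6.4.5 primary run alone

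*Protocol*

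**What the plan says.** **Protocol 6.3.2.2.** The food experiment is a blocked design: "Appetizing foods, bland foods and non-food objects will be presented in separate 15 second -blocks". Between blocks, "A 15 s rest period (fixation) will be intermixed between the stimulation blocks". On quantity, "A total of 10 blocks per condition will be run" and "Fifty images from each category will be used"; on length, "The experiment lasts about 15 minutes". The task is to report by button press which way each picture is displaced. On analysis: "The model includes four experimental conditions (appetizing foods, bland foods, objects, rest"). The section calls the specific effect of surgery on responses to high-calorie food its main interest, and assigns the test: "The appetizing food vs. objects and bland foods vs. objects contrasts will be used to assess" whether surgery lowers responses to appetizing foods alone. Section 3.2.3 states the matching hypothesis.

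**Protocol 6.4.5.** The primary fMRI experiment shows "alternating 16s blocks of appetizing, high-calorie and bland, low-calorie food pictures", with periodic ratings of hunger and heart rate, and lasts about 12 minutes. Objects appear with bodies and faces in two control experiments of similar design. Rest is mentioned only as a separate 10-minute resting-state block.

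**Protocol 6.4.1.** The stimulus list has foods, faces and bodies, but no objects.

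No section says which description governs, or that two different food experiments are intended.

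**The concern.** The descriptions differ in block length, conditions, rest, task and duration. This is not detail that a statistical analysis plan can settle later, because it fixes what is acquired. A condition or baseline that was never scanned in a run cannot be added at analysis.

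The conflict bears on one stated question: whether the change after surgery is confined to appetizing food. Appetizing versus bland cannot answer it, because a fall in the appetizing response and a rise in the bland response change that difference in the same direction. The food-type-by-group interaction in 6.4.5 has the same limit: a weaker bland response in patients would look like an enhanced appetizing response. The object contrasts are there to resolve this, and they need objects and food measured against a common reference.

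**Working it through.** **1. Is each description coherent on its own terms?**
- 6.3.2.2: 3 conditions × 10 blocks × 15 s = 450 s of stimulation. Thirty rests × 15 s = 450 s. Total 900 s = 15 min, as stated. Ten blocks × 5 pictures = 50 per category, also as stated.
- 6.4.5: 12 min = 720 s, and 720 / 16 = 45 blocks, or 22.5 per food type, if nothing else occupies the run. That is 360 s per food type, against 10 × 15 = 150 s in 6.3.2.2.

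The first script reproduces its own figures. The second cannot be the same run.

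**2. Can the object contrasts be formed?** Let A = appetizing, B = bland, O = objects, X = the other stimulus in the object run. A contrast c is estimable when c·X⁺X = c for design matrix X.
- 6.3.2.2, one run: A−B, A−O and B−O are all estimable.
- 6.4.5 primary run alone: A−B is estimable. A−O and B−O are not, because the run contains no objects.
- 6.4.5 food run plus object run, no within-run baseline, boxcar regressors: A + B equals the food-run constant and O + X equals the object-run constant. The six columns (four conditions, two constants) have rank 4, and A−O is not estimable.

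**3. First-level precision.** Inputs from the protocol: block lengths, TR 2.998 s (rounded to 3 s) and the 128 s high-pass filter. Assumptions: double-gamma haemodynamic response, one constant per run, independent errors with standard deviation sigma, randomly permuted block order for 6.3.2.2. SE = sigma × √(c(X′X)⁻¹c′).

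| Design | SE(A−B) | SE(A−O) |
|---|---|---|
| 6.3.2.2 | about 0.20 | about 0.20–0.21 |
| 6.4.5 food + object run, no baseline | 0.126 | 1.11 |
| as above, 5 s rating pause every 8 blocks | – | about 0.56 |
| as above, 10 s pause every 4 blocks | – | about 0.29 |
| as above, 16 s pause every 4 blocks | – | about 0.25 |
| 6.4.5 runs with 16 s fixation after every block | 0.18 | 0.22 |

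In the second row A−O is identified only by the signal rise at the start of each run. The pause rows treat the rating periods as unmodelled baseline. The protocol gives neither their length nor their spacing, so those values are assumptions. In the last three groups of rows A−O remains a comparison between runs.

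**4. The contrast list in 6.3.2.2.** It includes (1) appetizing versus bland and (3) both foods versus objects. With (3) averaged over the foods, A−O = (3) + ½·(1) and B−O = (3) − ½·(1). Both object contrasts therefore follow from the list, provided objects and foods are in the same model.

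**The case against.** The strongest reply is that the precision loss is inferred from silence. Section 6.4.5 does not say that fixation is absent or that food blocks fill the run, and its periodic ratings may interrupt the alternation. If so, A and B no longer sum to the run constant and the contrast with the object run becomes estimable, with an SE of about 0.25 to 0.56 rather than 1.11. This stands. It limits the size of the problem but does not remove it: a rating period is a task, not rest, and the contrast is still between runs.

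Second, the lead fMRI prediction in 3.2.3 and the group and surgery comparisons in 6.4.5 and 6.4.7 use appetizing versus bland, which is estimable under both versions and more precise under 6.4.5. This also stands. Only the specificity question is exposed, although 6.3.2.2 calls it the main interest.

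Third, these are first-level figures with independent errors, whereas the protocol plans AR(1) errors and a random-effects second level. No between-subject standard deviation is given, so the effect on group-level conclusions cannot be quantified.

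**Conclusion.** The contradiction is real and needs resolving before scanning. The four-condition model and both object contrasts cannot be formed from the 6.4.5 primary run alone. Recovering them across runs depends on a within-run baseline that 6.4.5 does not list. The first-level SE is then about 1.1 sigma with none (haemodynamic response included) and about 0.25 to 0.56 with assumed rating pauses, against about 0.2 in the 6.3.2.2 run.

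Three stronger readings are not supported:
- A reader might infer that the object contrasts cannot be estimated under 6.4.5 at all. Objects are shown elsewhere in the session, and the result turns on a baseline about which the text is silent. The variance ratio from the no-baseline case (1.22 / 0.043, about 28) is a worst case, not a property of the plan.
- A reader might infer that the fMRI hypotheses fail as a whole. Appetizing versus bland, with its group and pre/post comparisons, survives.
- A reader might infer that subjects or visits will be scanned on different versions. The protocol plans no such thing; the ambiguity only leaves it possible.

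**What to change.** Before scanning, state one governing food paradigm for all subjects and both visits. Two forms would work:
- Keep object and fixation blocks in the food run, as 6.3.2.2 already scripts, and remove the 16 s / 12 min description. Faces and bodies can remain separate runs.
- Keep the 6.4.5 alternation, but write explicit fixation blocks into every run, and state that food versus objects is then a between-run contrast.

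Align the model and contrasts in 6.3.2.2, the stimulus list in 6.4.1 and the description in 6.4.5 with the choice. Naming the two object contrasts in the first-level list is optional tidying.

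The cost is not zero. The first form takes 15 − 12 = 3 more minutes and raises the first-level SE of appetizing versus bland from about 0.13 to about 0.20 sigma. The second lengthens the runs or cuts stimulus time: with 16 s fixation after every block in a 12-minute run, 11 blocks × 16 s = 176 s per food type instead of 360 s.

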### 6.4.7. Predictions: fMRI

We predict that in the preoperative scan, the patients will show elevated responses to high vs. lowcalorie foods in the reward circuit (ventral striatum, amygdala, medial prefrontal cortex). However, this hyperactivation predicted to be abolished after weight loss surgery. Regarding MOR and  $D_2R$ , we hypothesize that increased anticipatory reward activity (as indexed by fMRI) due to foods in the ventral striatum is associated with decreased striatal MOR and  $D_2R$  density.

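### Protocol 6.4.5 reads the pre-operative food-type by group interaction as an enhanced response to appetizing foods, but the interaction shows only a larger appetizing-minus-bland difference in patients

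*Protocol*

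**What the plan says.** Section 6.4.5 names the pre-operative test, food type (appetizing or bland) by group (patients or controls), and states what it will show: testing the interaction between food type and "group (patients vs. controls) will reveal the components of the reward circuit that show enhanced responses to appetizing foods in obesity".

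Section 6.4.7 predicts that before surgery "the patients will show elevated responses to high vs. lowcalorie foods in the reward circuit", and then refers to the result by a stronger name, with "this hyperactivation predicted to be abolished after weight loss surgery".

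Section 6.3.2.2 gives the group comparison: "A mixed ANOVA will be used to assess whether the responses of the reward system are different in the experimental vs. in the control group". It names no patient-control comparison within one food type. It also says that "The appetizing vs. bland foods contrast is used to assess the activation of the reward system in the experimental groups"; that sentence concerns the experimental groups and does not itself state a patient-control conclusion. The same section names separate contrasts of appetizing food against objects and of bland food against objects, but uses them to judge whether surgery reduces responses to appetizing foods only. Its numbered list of first-level contrasts has a single object contrast, which pools the two food types.

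The stimulation design is described in two ways. In section 6.4.5 the primary experiment shows "alternating 16s blocks of appetizing, high-calorie and bland, low-calorie food pictures", and objects appear elsewhere: "In two control experiments, rewarding and nonrewarding control stimuli (bodies, faces and objects) will be presented using a similar design". In section 6.3.2.2 appetizing food, bland food and object blocks, with rest periods between them, belong to one run.

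**The concern.** The protocol ties a particular conclusion to a particular test, and the test cannot deliver it. The bland images are foods such as cabbage and lentils (section 6.3.2.2), so a weaker response to them in patients is a possible source of a positive interaction. A team that followed section 6.4.5 as written would report such a result as an enhanced response to appetizing foods.

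The label also carries forward. Section 6.4.7 predicts that the hyperactivation is abolished after surgery. If the baseline difference came from the bland side, a recovery of the bland response would be reported as the removal of over-responding to high-calorie food. The protocol sees this distinction for the surgical change: section 3.2.3 expects that change to come from appetizing food alone, and section 6.3.2.2 assigns the object contrasts to it. It does not apply the same care to the baseline comparison of obese and lean subjects.

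**Working it through.** **Inputs from the protocol.** 20 + 20 = 40 patients and 20 controls, alpha 0.05 (section 12.1). The protocol gives no effect size, SD, power or sidedness for the fMRI comparison, so there is no figure of its own to reproduce.

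**Identification.** Let A and B be the mean responses to appetizing and bland food. The interaction is

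I = (A_pat − B_pat) − (A_con − B_con) = (A_pat − A_con) − (B_pat − B_con).

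Only the difference between the two bracketed group effects enters. A rise of d in A_pat and a fall of d in B_pat give the same I. The conclusion rests on this algebra; the figures below only illustrate it.

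**Power, closed form.** Two-sample t-test on the difference score A − B in one region, two-sided 0.05, uncorrected, df = 40 + 20 − 2 = 58, critical t = 2.00. The assumed effect is d = 0.8 SD of the difference score. The noncentrality is 0.8 / √(1/40 + 1/20) = 2.92, and power is 0.82. For d = 0.5 and 1.0, power is 0.43 and 0.95. Each value is the same whichever food type produces I.

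**Simulation.** 20,000 trials per scenario, SD 1 per condition, within-subject correlation 0.5. The SD of the difference score is then √(2 × (1 − 0.5)) = 1, so I = 0.8 again means d = 0.8. The appetizing response is taken as measured directly, without added noise from a reference condition.

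| Patients relative to controls | Significant positive interaction | Significant positive group effect on appetizing response | Both |
|---|---|---|---|
| Appetizing +0.8, bland equal | 82% | 82% | about 72% |
| Appetizing equal, bland −0.8 | 82% | about 3% | about 2% |
| Appetizing −0.4, bland −1.2 | 82% | under 0.1% | under 0.1% |

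In the third row patients respond less to appetizing food, yet the wording of section 6.4.5 would report enhancement. With no group difference on either food, the interaction rejects in about 5% of trials, so the test itself is sound.

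**Stricter threshold.** Section 6.3.2.2 plans voxel-wise testing with Gaussian Random Field Theory. At an assumed two-sided voxel threshold of 0.001 (not stated in the protocol), power for d = 0.5, 0.8 and 1.0 falls to 6%, 31% and 58%. It falls equally for both sources of the interaction, so the ambiguity remains.

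**The case against.** The best defence is that the hypotheses are themselves differential. Section 3.2.3 expects the differential activity to be more pronounced in patients before surgery, and section 6.4.7 predicts a high-versus-low difference, to which its word hyperactivation refers back. The interaction tests exactly that. This stands, and it limits the point to the conclusion drawn from the test.

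A second defence is that section 6.3.2.2 models the conditions separately and names both object contrasts, and that breaking an interaction into simple effects is routine and often left to an analysis plan. It stands in part: under that design the ambiguity can be resolved. But the protocol did not leave the interpretation open. It wrote down a conclusion and reserved the separate contrasts for the surgery question.

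A reader might infer more than the documents support:

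- That 82% is the chance of a wrong report in this trial. It is power for a real interaction in one region without correction, under an assumed bland deficit for which the protocol offers no evidence. It says nothing about how likely that deficit is.
- That a lower bland response is the opposite of what was predicted. It is still a larger appetizing-bland difference, with another source.
- That this is the trial's central claim. Section 3.1 lists many objectives and names none as primary, and its fMRI item is framed as before and after surgery.
- That objects settle the matter. Comparing appetizing with objects between groups is again a difference of differences, and a lower object response in patients would raise it.

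**Conclusion.** The point holds as one of interpretation. A positive pre-operative interaction supports a larger appetizing-minus-bland difference in patients. It does not support an enhanced response to appetizing foods or hyperactivation without evidence on the appetizing response itself. This follows from the algebra and needs no assumption about effect size.

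The illustrative size is 82% for either source at 0.8 SD. It rests on a single region, an uncorrected two-sided 0.05 level, complete data on 40 and 20 subjects, and an assumed effect. Voxel-wise correction lowers both rates equally. Nothing here shows that the interaction is the wrong test or that the predicted hyperactivation is absent. The wording should be corrected before the data are read, at moderate priority.

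**What to change.** 1. In sections 6.4.5 and 6.4.7, keep the interaction as the test of a differential response, and word a positive result as a larger appetizing-bland difference in patients.
2. Allow the terms enhanced response to appetizing foods and hyperactivation only where patients also exceed controls, pre-operatively and in the same pre-defined region, on the appetizing response against a common reference. Use objects as that reference, with rest as a check, because a lower object response in patients would also raise the object contrast.
3. Report the patient-control bland contrast against the same reference beside it. Where only the bland response differs, say so.
4. Reconcile the two stimulation designs so that object and rest blocks lie within the food run. Section 6.3.2.2 has them there; section 6.4.5 read literally does not, so the extra contrasts come free only under the former.

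The cost is two or so further second-level contrasts and lower power for the stronger claim: in the simulated appetizing-only scenario, from 82% for the interaction alone to about 72% when both conditions must hold. Noise in the reference condition would lower it further.

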### 3.2.2. The main hypotheses of MRI/MRS

We predict that the liver and mediastinal fat content is effectively decreased due to surgery.

Brain white matter volumes among obese are expected to be larger and to decrease during surgeryinduced weight loss. The bone marrow fat content should decrease upon surgery induced weight loss.

3.2.3. The main hypotheses of the brain activation studies (fMRI) and molecular imaging studies (neurotransmitter PET):

We predict that the neural responses of the reward circuit (amygdale, ventral striatal and midbrain regions) will be decreased post-operatively for the appetizing vs. bland foods in surgical groups. The differential activity is expected to be more profound in the patient group before surgery vs. healthy controls [54]. This between-groups difference in the activity of the reward system is expected to diminish in the post-operative scan. Furthermore, it is expected that this change in responsiveness is due to decreased responses to appetizing food only. In addition the changes of brain activation due to surgery-induced weight loss are expected to correlate with changes in gastrointestinal hormone secretion and with subjective feelings of hunger. Obesity is predicted to be associated with lowered grey and white matter volume (as measured by voxel-based morphometry), as well as altered connectivity between the subcomponents of the reward circuit (as measured by diffusion tensor imaging).

We predict that striatal  $D_2$  receptors, as measured with [C]raclopride, are decreased in obese individuals in comparison with lean control subject, and that weight loss following surgery results in increase in the number of these receptors. This would be consistent with lowered sensitivity to actual food reward in obesity. These receptors are also expected to predict functional responses in fMRI, especially receptors in the ventral striatum. Given the role of  $\mu$ -opioid receptors in reward functions, we predict that these receptors are increased in the brain reward network in obesity, consistent with hypersensitivity to anticipatory reward in obesity. Again, these receptors are hypothesized to correlate with fMRI responses – and with dopamine  $D_2$  receptors. Finally, we predict that weight loss will normalize the brain opioid dysfunction in obesity.

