### 6.4.6. Predictions: D2R and MOR

For D2R, testing for the main effect of group (obese vs. lean) as well as the interaction between group (obese vs. lean) and measurement (pre- vs. postoperative) will reveal whether lower  $D_2R$  availability – particularly in the striatum - in obesity will be reversible upon successful weight loss following surgery. For MOR, testing for the main effect of group (obese vs. lean) and an interaction

between group (obese vs. lean) and measurement (pre- vs. postoperative) will reveal whether obesity is associated with higher MOR availability – particularly in the striatum - , and whether this will be reversible upon successful weight loss following surgery. Additionally, self-reported trait craving for foods will be correlated with striatal MOR density. In line with the animal work (69,105), we predict that food craving will be positively associated with MOR availability in the striatum.

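### The BOLD–D2R and craving–MOR correlations name no analysis set or group term; if obese and lean subjects are pooled, the predicted group differences alone can produce or mask the hypothesised associations

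*Protocol*

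**What the plan says.** Two associations are planned as plain correlations. In Protocol 6.4.5, "BOLD signal changes due to viewing appetizing and bland foods will be correlated with striatal" D2 receptor density. In 6.4.6, "self-reported trait craving for foods will be correlated with striatal MOR density". Neither sentence names the subjects, the scan, a covariate or a within-group analysis, and section 12.2 adds no model. The same two subsections do name group terms for other analyses: food type by group for the fMRI contrast (6.4.5), and group and group by measurement for receptor availability (6.4.6).

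The protocol also predicts how the groups differ:

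- D2R: striatal receptors "are decreased in obese individuals in comparison with lean control subject" (3.2.3).
- MOR: "we predict that these receptors are increased in the brain reward network in obesity" (3.2.3; repeated for the striatum in 6.4.6).
- BOLD: before surgery, "the patients will show elevated responses to high vs. lowcalorie foods in the reward circuit" (6.4.7).
- Craving: section 2.4.1 takes it to be elevated in obesity. This is a background premise; no group difference in craving is listed as a prediction.

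The hypothesised associations are negative for BOLD with both receptors, since "increased anticipatory reward activity (as indexed by fMRI) due to foods in the ventral striatum is associated with decreased striatal MOR" and D2R density (6.4.7), and positive for craving with MOR: "we predict that food craving will be positively associated with MOR availability in the striatum" (6.4.6).

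**The concern.** When two variables both differ between two groups, a correlation across the combined sample mixes the between-group gap with the association inside each group. Here the direction of the mixing follows from the protocol's own predictions. D2R lower and BOLD higher in the obese pushes the pooled BOLD–D2R correlation negative, which is the hypothesised sign. MOR higher with craving higher pushes craving–MOR positive, again the hypothesised sign. MOR higher with BOLD higher pushes BOLD–MOR positive, against the hypothesised sign.

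A pooled analysis could therefore report support for the first two hypotheses when receptor level says nothing about response or craving among people of the same group. It could also miss or reverse the third when that association is real. The reader could not tell a receptor–response relationship from a restatement of the obese–lean difference.

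A second problem lies in the stated directions. Section 3.2.3 presents increased MOR in obesity as fitting hypersensitivity to anticipatory reward. Section 6.4.7 ties greater anticipatory reward activity to decreased MOR.

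**Working it through.** **The plan's own figure.** Section 12.1 states that 20 + 20 patients and 20 controls suffice at alpha 0.05. It gives no effect size, SD or power, so it cannot be reproduced. For orientation, 40 against 20 has 80% power (two-sided 5%) for a group difference of about 0.77 SD.

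**Inputs from the protocol.** 40 obese, 20 lean, alpha 0.05, and the directions listed above.

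**Assumptions.** Two-sided tests; pooling of all 60 subjects; normal data with equal within-group SDs; the same standardised gap d in both variables. The protocol gives no gap sizes, so a range is shown.

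**Formula.** With obese fraction p = 40/60, p(1 − p) = (2/3)(1/3) = 0.222. For a within-group correlation ρw and gaps d1 and d2,

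pooled ρ = [ρw + 0.222·d1·d2] / √[(1 + 0.222·d1²)(1 + 0.222·d2²)].

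With ρw = 0 and both gaps equal to 1.0 in size, |ρ| = 0.222/1.222 = 0.18. At 0.5 it is 0.0556/1.0556 = 0.05, and at 1.5 it is 0.5/1.5 = 0.33.

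**Rejection rates**, by simulation (t test of r; 40,000 runs per setting), pooled and with group as a covariate:

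| Gap in both (SD) | Pooled \|r\| if ρw = 0 | False positives, pooled | False positives, group in model | Pooled BOLD–MOR r if ρw = −0.35 | Power for a negative result, pooled | Power, group in model |
|---|---|---|---|---|---|---|
| 0.5 | 0.05 | 7% | 5% | −0.28 | 58% | 79% |
| 0.8 | 0.12 | 16% | 5% | −0.18 | 28% | 79% |
| 1.0 | 0.18 | 29% | 5% | −0.10 | 10% | 79% |
| 1.2 | 0.24 | 48% | 5% | −0.02 | 3% | 79% |
| 1.5 | 0.33 | 78% | 5% | +0.10 | 0.1% | 79% |

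The false-positive columns apply to BOLD–D2R (negative sign) and craving–MOR (positive sign). From 0.8 SD upward nearly all the false positives fall in the hypothesised direction. The last three columns apply to the BOLD–MOR hypothesis; the value −0.35 is an assumption.

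**Cost of the extra term.** By Fisher's z, the correlation detectable with 80% power at n = 60 moves from 0.355 to 0.358.

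**The MOR direction.** If MOR and anticipatory BOLD are both higher in the obese, the between-group direction is positive, while 6.4.7 states a negative association. Both can be true only if the between-group and within-group directions differ. The protocol does not say so, and a correlation without a group term could not separate the two.

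**The case against.** **Pooling is not stated.** A reader might infer that the protocol fixes a pooled, unadjusted correlation. It does not: the analysis set is simply unnamed, and a statistical analysis plan, which is not at hand, could add a group term without contradicting the protocol. This stands, and it makes the harm conditional.

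**The sizes are assumed.** A reader might take severe inflation as established. It is not. At 0.5 SD the false-positive rate is only about 7%, and 48% or 78% needs gaps of 1.2 or 1.5 SD in both measures at once. This stands. However, if section 12.1 is read as 80% power for obese–lean differences, the gaps counted on are about 0.77 SD, where pooled error is already roughly three times nominal.

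**Craving and BOLD–MOR are less firmly specified.** The craving difference is background only, and BOLD–MOR is a hypothesis without a stated analysis. Both limits stand.

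**Adjustment is not neutral.** If low D2R and a high BOLD response are each causes of obesity, selecting groups on BMI makes group a common effect, and conditioning on it induces a correlation. In one such model (independent causes, 40 subjects from the top 5% of liability and 20 from the bottom half), at gaps of about 0.86, 1.15 and 1.43 population SD, the adjusted test rejects in 9%, 22% and 49% of runs and the pooled test in 11%, 17% and 36%. Within-group estimates are affected as well. This is a fair caution about interpretation, since the protocol leaves open whether brain differences are causes or consequences. But it needs that particular causal model, and the pooled test is biased under it too, so it does not rescue an unadjusted correlation.

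**Low rank.** Receptor–fMRI and receptor–craving correlations are not among the numbered objectives in 3.1. That limits the weight of the point; it does not remove it.

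**Conclusion.** The point holds as a conditional one. The two correlations are planned without an analysis set or group term. If obese and lean subjects are combined, the protocol's predicted differences can create the hypothesised BOLD–D2R and craving–MOR correlations with no within-group association, and can hide the hypothesised negative BOLD–MOR one. The effect is slight at gaps of 0.5 SD and large from about 1.0 SD, on the assumptions of equal gaps, two-sided 5% tests and all 60 subjects contributing. The documents do not support saying that a pooled analysis is planned, that the group gaps are of any given size, or that craving is formally predicted to differ. The adjusted test keeps its 5% level when receptor and outcome are independent given group; it does not make the association causal.

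The conflict over the MOR–BOLD direction between 3.2.3 and 6.4.7 is in the text itself and needs resolving whatever a separate analysis plan contains.

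**What to change.** In sections 6.4.4 to 6.4.7, state that any correlation using both obese and lean subjects is computed on the preoperative (baseline) scan with group as a covariate, as a partial correlation or a regression containing group. Show the estimates within the obese and within the lean groups alongside. State that all are read as associations given group, not as causal effects.

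Reconcile 3.2.3 with 6.4.7 on MOR and anticipatory reward activity: either give one direction, or say that the between-group and within-group directions are expected to differ.

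The cost is a few sentences, one model term and one degree of freedom. No extra subjects or scans are needed. The within-group estimates will be imprecise (80% power only for |r| of about 0.43 at n = 40 and 0.59 at n = 20), so they serve as description beside the adjusted estimate.
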